##### 2) Justification:

The calculation of the sample size was conducted using G\*Power (version 3.1.9.7) to enable comparative studies among patient groups with statistical significance. For this study, we aimed for an effect size of 0.25, significance level  $\alpha$  error probability of 0.05, and power (1- $\beta$  error probability) of 0.95. This calculation resulted in a required sample size of 417 cases per group, totaling 834 samples. Considering a potential loss rate of 20% in the collection of the primary sample, feces, we aimed for 500 cases per group, resulting in a total of 3,000 samples across the three liver disease groups.

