#### C. Sample Size and Justification

##### 1) Sample Size: Total of 3,000 cases

Autoimmune Liver Diseases (patients diagnosed with autoimmune hepatitis, primary biliary cholangitis, primary sclerosing cholangitis): Experimental group 500 cases, Cohabitants control group 500 cases.

Metabolic Liver Diseases (patients diagnosed with non-alcoholic fatty liver disease): Experimental group 500 cases, Cohabitants control group 500 cases

Infectious Liver Diseases (patients diagnosed with liver abscess): Experimental group 500 cases, Cohabitants control group 500 cases

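### The 20% loss allowance is applied the wrong way: 500 per group leaves 400, below the protocol's own requirement of 417

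*Protocol*

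**What the plan says.** The Justification in Protocol section 3.C.2 goes in three steps. The inputs are an alpha of 0.05, a power of 0.95 and an effect size: "For this study, we aimed for an effect size of 0.25". The result is given as "This calculation resulted in a required sample size of 417 cases per group, totaling 834 samples". The allowance for lost stool samples follows: "Considering a potential loss rate of 20% in the collection of the primary sample, feces, we aimed for 500 cases per group". The paragraph closes with an overall figure of 3,000.

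Section 3.C.1 carries the same number forward under "Sample Size: Total of 3,000 cases": 500 patients and 500 cohabitants in each of three disease categories, so six groups of 500.

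The protocol gives no other loss rate or inflation rule, and does not say that lost participants will be replaced. Section 5.B allows a patient to be registered alone when the cohabitant declines or the patient lives alone. That concerns who is enrolled and does not replace a lost stool sample.

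**The concern.** A loss allowance exists so that the required number is still there after the losses. Here the required number, the loss rate and the enrolment target all stand in one paragraph, and a single multiplication shows that the target does not protect the requirement at the stated rate. If so, the 95% power that produced the 417 is not preserved at the loss the protocol itself plans for, and section 3.C.1 repeats the affected target in every group.

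**Working it through.** **Inputs, all from section 3.C.2:** effect size 0.25; alpha 0.05; power 0.95; required n = 417 per group (834 for two groups); loss rate 20%; planned enrolment 500 per group. Section 3.C.2 does not state the test, its sidedness or the type of effect size.

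**Step 1. Reproduce the 417.** Take a two-sample t-test with equal groups, two-sided alpha 0.05 and standardised mean difference d = 0.25.

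- Normal approximation: n = 2 × (1.960 + 1.645)² / 0.25² ≈ 415.8 per group.
- Noncentral t: n = 416.8, so 417. Power is 0.9496 at 416 and 0.9501 at 417.
- Total: 2 × 417 = 834, as stated.

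Other readings of the effect size do not give 417: a one-sided t-test gives 347 per group, a two-group analysis of variance with f = 0.25 gives 105 per group, and a paired t-test with a standardised difference of 0.25 gives 210 pairs. The two-sided t-test with d = 0.25 is therefore inferred from the match.

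**Step 2. Apply the loss.** This step uses printed figures only.

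- Evaluable at 20% loss: 500 × (1 − 0.20) = 400.
- Shortfall: 417 − 400 = 17 per group, or 17/417 = 4.1%.
- Largest loss that 500 can absorb: 1 − 417/500 = 0.166, or 16.6%.

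**Step 3. Where 500 probably comes from.** 417 × (1 + 0.20) = 500.4, which rounds to 500. The protocol shows no formula, so this is the likeliest explanation and not a stated one.

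**Step 4. Enrolment that would retain 417 at 20% loss.** 417/(1 − 0.20) = 521.25, so 522. Check: 522 × 0.80 = 417.6, which suffices; 521 × 0.80 = 416.8, which does not. Over six groups, 522 × 6 = 3,132 against 3,000.

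**Step 5. Effect on power.** Same t-test as in step 1, with 500 enrolled per group:

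| Loss | Evaluable per group | Power |
|---|---|---|
| 0% | 500 | 0.977 |
| 10% | 450 | 0.963 |
| 15% | 425 | 0.953 |
| 16.6% | 417 | 0.950 |
| 17% | 415 | 0.949 |
| 20% | 400 | 0.942 |

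With 400 per group, the smallest effect detectable with 95% power is d = 0.255 instead of 0.250.

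**The case against.** The strongest objection is that this hardly matters. Power falls by about 0.8 percentage points and the detectable effect moves from 0.250 to 0.255. The protocol describes the loss as potential and the 500 as an aim, which is how one writes a rounded planning target in an observational sample-collection study. This stands, and it limits the point to a minor one. It does not remove it: rounding explains 500.4 becoming 500, but not 522 becoming 500.

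A second objection is that the protocol never states the power for 500 enrolled with 20% lost; 0.95 is only the input that gave 417. That is correct as a reading of the text. Still, an allowance for loss has no purpose except to keep the required number, and with it the power behind that number.

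Third, the power figures describe a two-sample t-test, whereas the Statistical Analysis Methods in section 4 plan LDA effect size or MaAsLin2 for the stool taxa and name t-tests for continuous transcriptome and metabolome variables. This stands too. The 94.2% checks the protocol's calculation against itself and is not the power of the planned stool analysis. The comparison of 400 with 417 does not depend on the choice of test.

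The only reading under which 500 suffices is that 20% means extra recruitment on top of 417. The text calls it a loss rate in stool collection, so that reading does not fit.

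**Conclusion.** The point holds, as a minor arithmetic error. At the protocol's own 20% loss, 500 enrolled per group leaves 400, which is 17 below its own requirement; 500 covers losses up to 16.6%, and 522 would be needed for 20%. These figures rest only on numbers printed in section 3.C.2 and on the absence of any replacement rule. The consequence for power, 94.2% in place of 95%, additionally assumes a two-sided two-sample t-test with d = 0.25. That inference is well supported because it reproduces 417 exactly, but the protocol does not state it. No design decision turns on the difference.

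**What to change.** Keep 500 per group and replace the loss sentence in section 3.C.2, for example with:

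> Enrolling 500 per group retains the required 417 for losses of stool samples up to about 16.6%. At a 20% loss, 400 evaluable per group give about 94% power for the two-group calculation above (two-sample t-test, standardised difference 0.25, two-sided alpha 0.05).

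The sponsor should confirm the content of the bracket from the G*Power record before it becomes protocol text. The cost is one sentence. No further participants are needed, and section 3.C.1 stays as it is.

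If the sponsor prefers to hold 95% power at a 20% loss, the matching enrolment is 522 per group and 3,132 in total, which is 132 more participants, and section 3.C.1 must change with it. The gain of 0.8 percentage points in power hardly justifies that.

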## 4. Method

### 1) Sample Collection and Storage

#### [Fecal Samples]

Participants who have consented to this study will provide 5cc of feces using the following kit: Samples obtained from patients and cohabitants will be stored in a designated freezer maintained at -80°C, equipped with a security device, at a specific location. Each sample will be assigned an encrypted sample number. Upon usage, the entry and exit of samples will be recorded by a designated manager. Once the experiment objectives are achieved, all samples will be disposed of appropriately.

#### [Blood Samples]

Participants who have consented to this study will provide 20cc of blood via venipuncture from the arm into EDTA and SST bottles as follows: Samples obtained from patients will undergo peripheral blood mononuclear cell isolation within 24 hours using plasma and Ficoll density gradient separation. These samples will be stored in a designated freezer maintained at -80°C, equipped with a security device, at a specific location. Each sample will be assigned an encrypted sample number. Upon usage, the entry and exit of samples will be recorded by a designated manager. Once the experiment objectives are achieved, all samples will be disposed of appropriately.

Fig 1. Stool kit

### 2) Analytical Methods

From collected fecal samples, bacterial DNA will be extracted using a DNA extraction kit, followed by 16S ribosomal RNA gene amplicon sequencing. Peripheral blood mononuclear cells will undergo total RNA extraction using an RNA extraction kit, followed by RNA sequencing. Plasma samples will undergo metabolite measurement using LC-MS or NMR.

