### 3) Integrated Analysis with Clinical Data

Clinical data will be utilized to stratify or classify patient groups, and sequencing results will be integrated to identify disease-specific gut bacteria.

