### \* Observational Items, Clinical Examination Items, and Observation Methods

- Basal characteristics (age, gender, chief complaints, weight, past medical history, present illness, family history, alcohol consumption, smoking history)
- Hematological and serological/immunological markers (complete blood count results, serum alkaline phosphatase, AST, ALT, gamma-GT, total bilirubin, glycated hemoglobin, fasting blood glucose, lipid profile, IgM, IgG, antinuclear antibodies, anti-smooth muscle antibodies, anti-mitochondrial antibodies, HBsAg, HBeAg, HBcAg, HBs-Ab, anti-HBe, anti-HCV status)
- Imaging findings (CT scan, MRI, abdominal ultrasound, endoscopic retrograde cholangiopancreatography (ERCP) if applicable)
- Histopathological findings (pathological findings of liver biopsy tissue if applicable)

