### 4) Statistical Analysis Methods

Statistical analysis for the results of microbial species and distribution will involve Taxonomic profiling using the Galaxy platform, followed by LDA analysis. Grouping by primary diagnosis and deriving LDA Effect Size or utilizing MaAsLin2 functionality to identify taxa showing significant compositional changes between diseases. For transcriptome and metabolome results, categorical variables will be analyzed using the Chi-square test, while continuous variables will undergo t-tests. Correlation analysis will employ Pearson's coefficient.

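### The transcriptome comparison uses unadjusted t-tests on RNA from mixed mononuclear cells, so if cell mix differs between disease groups it can appear as altered gene expression; a composition-adjusted model beside it is a cheap improvement

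*Protocol*

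**What the plan says.** **Specimen.** The Protocol, section 4, 1) Sample Collection and Storage, [Blood Samples], states: "Samples obtained from patients will undergo peripheral blood mononuclear cell isolation within 24 hours using plasma and Ficoll density gradient separation". No sorting or enrichment of a cell type is described, and the sentence names patients only.

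**Assay.** Section 4, 2) Analytical Methods: "Peripheral blood mononuclear cells will undergo total RNA extraction using an RNA extraction kit, followed by RNA sequencing". This is one bulk measurement per sample on a mixture of cell types.

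**Test.** Section 4, 4) Statistical Analysis Methods: "For transcriptome and metabolome results, categorical variables will be analyzed using the Chi-square test, while continuous variables will undergo t-tests". No covariate, cell-composition term or deconvolution step is named for these data.

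**Blood count.** The list of observational and clinical examination items includes "complete blood count results". It does not say whether a differential is recorded.

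**Use of clinical data.** Section 4, part 3) on integrated analysis, gives their purpose as follows: "Clinical data will be utilized to stratify or classify patient groups, and sequencing results will be integrated to identify disease-specific gut bacteria". That describes grouping patients and finding bacteria. It does not describe adjusting expression for cell mix.

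**The concern.** In bulk RNA from a cell mixture, the measured level of a transcript made by only one lineage is roughly its expression per cell times that lineage's share of the mixture. A two-group t-test on the measured level sees only the product. If one disease group carries relatively more monocytes among its mononuclear cells, transcripts typical of monocytes will look raised and those typical of lymphocytes lowered, even if no cell has changed its expression.

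The comparison at issue is between autoimmune disease, fatty liver disease and liver abscess. The Background says that the study is meant to inform etiology and progression along the gut-liver axis. If the transcript list were led by genes that mark cell types, it could be read as altered gene regulation when a cell count would have shown the same thing. Because the protocol names the test, an analysis plan that follows it would carry the ambiguity forward.

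**Working it through.** **1. The protocol's own figure.** Section 3.C gives "we aimed for an effect size of 0.25", alpha 0.05, power 0.95 and 417 per group. With the normal approximation, n = 2(1.960 + 1.645)²/0.25² ≈ 416. The exact noncentral t gives 417 (power 0.9501). A one-sided test would give 347. So 417 is a two-sided, two-sample t-test with a standardised difference d of 0.25, and that figure is not in dispute here. It is a useful yardstick: the design is sized to detect d = 0.25, whatever causes it.

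**2. Monocyte-restricted transcript, no change per cell.**

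Inputs:
- Group size 400 v 400, from 500 × (1 − 0.20). The protocol applies the 20% loss to stool, so using it for RNA is an assumption.
- Monocyte share of mononuclear cells: 20% in one group and f in the other. Assumption; the documents give none.
- Between-person SD of log expression: 0.7 (natural log). Assumption.

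Formula: d = ln(f/0.20)/SD. The rejection rate is approximately Φ(d√(400/2) − 1.960).

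| Shares | d | d√200 | Rejection at 0.05 |
|---|---|---|---|
| 20% v 20% | 0 | 0 | 5% |
| 20% v 22% | 0.0953/0.7 = 0.14 | 1.93 | 49% |
| 20% v 25% | 0.2231/0.7 = 0.32 | 4.51 | 99.5% |
| 20% v 30% | 0.4055/0.7 = 0.58 | 8.19 | about 100% |

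At 20% v 25%, changing the SD from 0.5 to 1.0 moves d from 0.45 to 0.22 and rejection from 100% to 88%. At a much stricter alpha of 2.5e-6 (assumed), rejection at 20% v 25% is still 42%, so a multiplicity correction would reduce the problem but not remove it.

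**3. Transcripts that differ less by lineage.** A simulation used 417 per group, 1000 runs per setting and no per-cell difference between groups. Expression was y = log2(mR + 1 − m) + error. Here m is the monocyte share (SD 0.06), R is the monocyte-to-lymphocyte expression ratio, and the error SD is 0.5 log2 units. All of these except the group size are assumptions. Rejection at 0.05 by the plain t-test:

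| Shares | R = 1 | R = 2 | R = 5 | R = 20 |
|---|---|---|---|---|
| 20% v 20% | 0.05 | 0.04 | 0.04 | 0.05 |
| 20% v 22% | 0.04 | 0.12 | 0.38 | 0.77 |
| 20% v 25% | 0.05 | 0.40 | 0.99 | 1.00 |
| 20% v 30% | 0.05 | 0.92 | 1.00 | 1.00 |

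Two conditions must both hold for the effect to arise: the mix differs between groups, and the transcript differs by lineage.

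**4. What adjustment achieves.** With m added as a covariate and known exactly, rejection was 0.04 to 0.06 in every setting. The simulation standard error at 0.05 is √(0.05 × 0.95/1000) = 0.007. With m measured with error (SD 0.03), the rates for R = 2, 5 and 20 were 0.07, 0.14 and 0.28 at 20% v 25%, and 0.08, 0.26 and 0.50 at 20% v 30%. Adjustment helps a great deal, but it is incomplete when shifts are large and the share is noisy.

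**The case against.** The strongest reply is that a t-test on bulk abundance is a valid test of bulk abundance. The protocol nowhere promises a per-cell comparison, and a shifted cell mix may itself be part of the disease. This stands. The unadjusted comparison should therefore be kept, and the point concerns interpretation, not the test's validity.

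Second, no figure for cell mix comes from the documents. This also stands. A reader might infer that the three diseases are bound to differ in mix, because the Background mentions immunosuppressants for two of the cholestatic diseases and because liver abscess is an infection. The protocol contains no data on cell shares, and its first sample is taken at diagnosis. The point must stay conditional.

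Third, a reader might infer that the needed measurement is already in hand. The document lists a complete blood count but not a differential, and without one the lymphocyte and monocyte shares are unknown.

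Fourth, a reader might extend the point to healthy cohabitants as controls. The selection criteria set no health requirement for cohabitants, and mononuclear-cell isolation is described for patients only. Only the disease-group comparisons are clearly affected.

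Finally, stool is the primary sample, and covariates for a supporting assay are often left to the analysis plan. That lowers the priority. It does not remove the point, because the protocol itself names a specific test for these data.

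**Conclusion.** The point holds as a conditional, low-cost improvement. The protocol pairs bulk RNA from unsorted mononuclear cells with an unadjusted t-test, and at its planned group size that test cannot distinguish altered regulation from altered cell mix in lineage-biased transcripts. Under the assumptions shown, a shift of five percentage points in monocyte share produces d = 0.32 for a monocyte-restricted transcript. That exceeds the 0.25 the study is sized to detect, and it is declared significant 99.5% of the time. A two-point shift gives 49%, and no shift gives the nominal 5%. A twofold lineage difference gives 40% at the five-point shift, and a transcript expressed equally in both lineages is unaffected.

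The documents do not support the stronger conclusions that the transcriptome results will be wrong, that the mix is known to differ, or that the t-test is invalid.

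**What to change.** In section 4, 4) Statistical Analysis Methods, keep the unadjusted comparison for transcripts and add:

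- A linear model on log-normalised expression with disease group and one composition covariate, monocytes/(monocytes + lymphocytes), from the blood count of the same visit if it includes a differential. If it does not, use cell fractions estimated from the RNA data by deconvolution.
- Use one covariate, not two. Monocyte and lymphocyte shares of that sum add to one, so both cannot be fitted with an intercept. Shares of all white cells would also move with neutrophils.
- Report both results side by side. Describe transcripts whose difference disappears after adjustment as possibly reflecting cell composition rather than gene regulation. Do not treat persistence after adjustment as proof of altered regulation, since a noisy covariate left rejection as high as 0.50 in the simulation.
- Apply this to the disease-group comparisons, and to cohabitants only if they also have mononuclear-cell RNA sequencing. The protocol should say whether they do.

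**Cost.** Analysis wording, plus confirming whether a differential is recorded at each sampled visit. The adjusted result answers a different, per-cell question and may remove disease-related shifts in cell mix. A blood count is also only a proxy for the mix in the isolated cells, and it does not separate T, B and NK cells, so the correction is partial.

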#### ■ The Utility of Gut-Liver Axis Research for Chronic Intractable Liver Diseases

- ▷ The gut-liver axis refers to bidirectional communication between the liver and gastrointestinal tract mediated by various signaling molecules and cellular pathways. The gut microbiome can regulate liver function and metabolism through the production of diverse metabolites such as short-chain fatty acids and bile acids. Conversely, the liver generates bile secreted into the intestine to aid in fat digestion and absorption, and bile acids also act as signaling molecules that can modulate gut microbiota and intestinal immune function.
- ▷ Dysregulation of the gut-liver axis has been implicated in the onset of non-alcoholic fatty liver disease (NAFLD) and inflammatory bowel disease (IBD), and understanding the underlying mechanisms mediating this interaction could lead to the development of novel therapies targeting specific pathways associated with the gut-liver axis.
- ▷ Therefore, this study aims to identify specific gut microbiome profiles unique to patients with chronic intractable liver diseases and to conduct gut-liver axis research related to etiology and disease progression.

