#### 2. Data collection method

We will collect a total of 20cc of venous blood and 5cc of stool (using a stool collection kit) from each consenting participant (patients and cohabitants living together) at three time points: at the time of the patient's disease diagnosis, 3-6 months after the patient's disease treatment, and 6-12 months after the patient's disease treatment.

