## Risks of the Study

- The blood collection procedure in this study is conducted similarly to routine clinical practices, typically involving approximately 30ml of blood (20ml for research and 10ml for routine tests). This amount is minimal and poses little risk to the patient's safety (less than 1/500th of the total blood volume in the body, equivalent to less than 1/25th of a typical blood donation).
- However, depending on the individual condition of the participant, symptoms such as dizziness, nausea, or vomiting may occur during blood collection. In such cases, the collection will be immediately discontinued, and measures such as intravenous hydration and bed rest will be provided to ensure stability.
- Additionally, for elderly participants aged 65 and above, the study protocol will involve explaining the research purpose, background, and methods in simple terms and allowing sufficient time to obtain informed consent.
- Furthermore, if applicable, guardians or representatives will also be provided with detailed explanations of the study's purpose, background, and procedures to obtain their consent.

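### The protocol sets no fasting condition and records no time since last meal for the research blood used for plasma metabolites, so a meal-state imbalance could be read as a disease difference and could not be corrected later

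*Protocol*

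**What the plan says.** The research blood is specified in several places in the protocol.

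- **Section 2, Data collection method:** both groups, patients and their cohabitants, give blood and stool. The schedule is "at three time points: at the time of the patient's disease diagnosis, 3-6 months after the patient's disease treatment". The last collection falls 6-12 months after treatment.
- **Section 4, 1), Blood Samples:** participants "will provide 20cc of blood via venipuncture from the arm into EDTA and SST bottles as follows". A 24-hour window for separating cells and plasma and a -80°C storage temperature follow.
- **Section 4, 2), Analytical Methods:** "Plasma samples will undergo metabolite measurement using LC-MS or NMR". No analyte is named.
- **Section 4, Observational Items:** the laboratory list includes "glycated hemoglobin, fasting blood glucose, lipid profile". This is the only mention of fasting. No item covers time since last meal.
- **Section 4, 4), Statistical Analysis Methods:** continuous transcriptome and metabolome variables are analysed by t-tests. No covariate is named for them.
- **Section 4, 7), Risks of the Study:** collection is described as "approximately 30ml of blood (20ml for research and 10ml for routine tests").

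**The concern.** Volume, tubes, processing window, visits and assay platform are all fixed. The participant's meal state at the draw is neither fixed nor recorded. By specifying a fasting glucose, the protocol itself accepts that a blood analyte can depend on recent food.

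An unadjusted t-test attributes any mean difference to the grouping variable. If one group has more fed samples than another, the meal effect enters the comparison in full. A larger sample does not dilute this bias; it makes a false difference more likely to reach significance.

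The protocol gives some reason to think the fed share could differ:

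- A patient's research tubes may be filled alongside routine fasting tests. Cohabitants are given no instruction to fast, and living in the same household does not equalise time since last meal at the draw.
- Three quite different diseases are sampled, first at diagnosis and again after treatment, so circumstances at the draw may differ by disease and by visit.

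This cannot be left to a statistical analysis plan. If meal state is not recorded at the draw, no later analysis can adjust for it.

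**Working it through.** **1. The plan's own figure.** Section 3.C.2 gives an effect size of 0.25, alpha 0.05, power 0.95 and 417 per group. A two-sided two-sample t-test (noncentral t, d = 0.25 taken as a standardised mean difference) gives 417 per group with power 0.9501. The normal approximation gives 416. The figure reproduces, and 417 per group is used below.

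**2. Inputs the protocol does not give.** Both are assumptions, and both are varied:

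- m, the meal effect on a metabolite, in SD: 0.25, 0.5, 1.0;
- q, the difference between two groups in the share of fed samples: 0, 10, 20, 30 percentage points.

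**3. Formula.** With a true disease effect of zero, the spurious standardised difference is d = m × q. The noncentrality of the t-test is d × √(417/2) = d × 14.44. The false-positive rate is the two-sided rejection probability at alpha 0.05 with 832 degrees of freedom.

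For m = 0.5 and q = 0.20, d = 0.10, the noncentrality is 1.44 and the rejection probability is 0.30.

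**4. Results: false-positive rate per metabolite at 417 per group.**

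| Meal effect m | q = 0 | q = 10 points | q = 20 points | q = 30 points |
|---|---|---|---|---|
| 0.25 SD | 0.05 | 0.065 | 0.11 | 0.19 |
| 0.5 SD | 0.05 | 0.11 | 0.30 | 0.58 |
| 1.0 SD | 0.05 | 0.30 | 0.82 | 0.99 |

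With equal fed shares the rate stays at its nominal 0.05.

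**5. Sensitivity to the formula.** Mixing fed and fasted samples also widens the SD, by a factor √(1 + m² × mean of p(1−p)), where p is the fed share in each group. Since p(1−p) is at most 0.25, the factor is at most √1.0625 = 1.031 at m = 0.5 and √1.25 = 1.118 at m = 1.0. Dividing d by these limits lowers 0.30 to no less than 0.29 (m = 0.5, q = 20 points) and 0.99 to no less than 0.97 (m = 1.0, q = 30 points). The conclusion does not change.

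**6. One case with explicit shares.** Take 20% fed in one group and 50% in the other, with m = 1. The mean of p(1−p) is (0.16 + 0.25)/2 = 0.205, so d = 0.30/√1.205 = 0.27. With 400 per group (500 less the 20% loss allowance), the t-test rejects about 97% of the time. At m = 0.5, d = 0.15 and it rejects about 54% of the time. A 30-point difference is the largest in the table, so these figures lie towards the upper end.

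**The case against.** **No imbalance is shown.** This is correct. The protocol gives neither fed shares nor a meal effect. Describing research and routine blood together, with fasting glucose on the list, suggests that some research tubes may be drawn fasted. But the protocol does not say so, and does not say that cohabitants have the same routine tests. If only patients are drawn fasted, the imbalance becomes systematic.

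**Bile acids.** A reader might infer that plasma bile acids are to be measured and are especially exposed. The documents do not support this. The background describes the microbiome acting on the liver "through the production of diverse metabolites such as short-chain fatty acids and bile acids", but the analytical section names no analyte.

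**Integrated analysis.** A reader might also infer that meal effects would produce false links between metabolites and taxa there. Section 4, 3) integrates clinical data with sequencing results and does not mention metabolites. The Pearson correlations in Section 4, 4) name no pair of variables.

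**Which groups are compared.** The processing text for plasma and cells refers to samples from patients, and the metabolome t-tests name no groups. A patient-cohabitant contrast is therefore not certain. The point does not depend on it, because meal state can also differ between diseases or visits.

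**The 0.25 benchmark.** The sample-size section calls stool the primary sample and does not tie 0.25 to metabolites. A spurious difference near 0.25 is a matter of scale only.

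**It may be handled elsewhere.** Draw conditions can sit in a laboratory manual, which is not at hand. But this protocol goes into enough detail to state tubes and processing time, and the missing data item is in its own list.

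**Burden.** Three visits for 3,000 participants is up to 3,000 × 3 = 9,000 draws, and a fast is hard to arrange at diagnosis. This stands, and it is why the fix asks for fasting only where feasible.

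**Conclusion.** The concern holds as a gap in what is collected and analysed. Followed as written, the plan cannot separate meal state from disease in the metabolome comparisons, and the loss cannot be recovered after collection. It is not a demonstrated bias: nothing in the protocol establishes that fed shares will differ.

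The size depends entirely on the two assumed inputs. Across meal effects of 0.25 to 1.0 SD and fed-share differences of 10 to 30 points, the per-metabolite false-positive rate at 417 per group runs from barely above nominal to near certainty, with 0.30 in the middle of the grid. The width of that range is itself a reason to record meal state.

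The consequence is confined to the plasma metabolite layer. Nothing here calls the stool sequencing into question. This is a cheap and worthwhile improvement, not a defect that stops the study.

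**What to change.** 1. **Sections 2 and 4, 1), and the Observational Items list:** record hours since last meal at every research draw, for patients and cohabitants at all three visits.
2. **Sections 2 and 4, 1):** take the research blood fasted where feasible, together with the fasting glucose draw where one is taken. If a participant has not fasted, still take the sample and flag it.
3. **Section 4, 4):** adjust metabolite comparisons for fasting status, and repeat them in fasted samples only.

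**Cost:** one recorded item, one instruction to participants and a change to the analysis text. No extra draw or assay is needed. Some visits will need scheduling, and some samples, especially at diagnosis, will be flagged as non-fasted, which makes the fasted-only analysis smaller. If fasting proves impractical, item 1 alone still makes adjustment possible at almost no cost.
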